Title: Regional Blockade of the Sternum with Liposomal Bupivacaine Prior to Incision Decreases Opioid Use in Patients undergoing Cardiac Surgery

Personnel:

- a) Principal Investigator: [name]
- b) Sub-Investigators:
 - i) [name]
 - ii) [name]
 - iii) [name]
 - iv) [name]
 - v) J. [name]
 - vi) [name]
 - vii) [name]
 - viii) [name]
 - ix) [name]
 - x) [name]
 - xi) [name]
 - xii) [name]

Background:

Prolonged and excessive narcotic usage in the postoperative setting has been linked to multiple complications. Use of complimentary pain management techniques such as regional analgesia can reduce postoperative pain and narcotic usage. This can enhance patient recovery and improve quality of life in the immediate postoperative period. [1] Previous research investigating the benefits of local analgesia during cardiac surgery have been limited by the sparse amount of single-center randomized controlled trials, particularly evaluating the use of para-sternal injections.

Of the available studies, the use of local analgesia injections compared to controls has led to improved pain scores and overall decreased perioperative opioid usage. Studies have shown this efficacy using 0.2% ropivacaine, [2] 0.75% ropivacaine, [3] and 0.53% liposomal bupivacaine [4] all compared to control groups receiving normal saline injections in the para-sternal area. These studies all used injections just prior to sternal closure and no significant evidence is available for the use of ultrasound-guided regional block of the sternum prior to surgical incision. Injection of analgesia prior to surgical incision has been shown to decrease postoperative pain compared to injection after surgical closure. [5]

Hypothesis/Aims:

We hypothesize that injection of 1.3% liposomal bupivacaine and 0.5% bupivacaine (20mL dose) as a sternal block prior to surgical incision will lead to decreased pain and opioid usage in the intraoperative and postoperative setting for patients undergoing upper mini- and median sternotomy compared to controls (normal saline block).

Aim 1: To demonstrate decreased postoperative opioid usage and decreased pain scores in the postoperative setting in the treatment group compared to controls.

The amount of opioid medications used will be recorded during the routine postoperative course. Pain scores, set by a validated system, will be obtained daily during the routine postoperative course.

Aim 2: To demonstrate decreased intraoperative opioid usage in the treatment group compared to controls

Aim 3: To demonstrate improvement in key clinical components closely linked to narcotic usage.

Multiple variables specific to opioid usage will be recorded during the routine postoperative setting. These included, but are not limited to: time to extubation, incentive spirometer volume, return of bowel function, postoperative atrial fibrillation incidence, delirium and intensive care unit (ICU) and overall lengths of stay (LOS).

Methods

This is an investigator-initiated prospective randomized study with an 18-month patient accrual period and patient follow-up period dependent on postoperative length of stay following surgery.

Regional Block: Liposomal Bupivacaine (1.3%) solution (20 mL dose) is proposed for use during this study. This solution has demonstrated increased efficacy in prolonged analgesia following injection. This solution will be injected as an ultrasound-guided subpectoral interfacial plane block.

Normal Saline: Normal saline (0.9%) will be used as the control solution for patients not receiving the liposomal bupivacaine solution. Injection procedure of this solution will be identical to that of the liposomal bupivacaine solution.

Procedures: Patients undergoing a surgical procedure through mini- or full sternotomy will be considered for inclusion in this study. Qualified patients will be randomized 1:1 to a liposomal bupivacaine sternal block or a normal saline block. An unblinded research coordinator will use a password-protected spreadsheet to randomly generate the subject's randomization assignment. The unblinded coordinator will communicate the information to the unblinded anesthesiologist who will perform the block. This ensures the intraoperative (including a blinded anesthesiologist and surgeon) and postoperative staff (including the blinded research coordinator) will remain blind to the randomization assignment. The subject will also be blinded to the assignment. The amount of opioid medications given by the anesthesia team during the procedure will be recorded. Anesthesiologists will be encouraged to standard of care early extubation. There will be no deviation from routine surgical procedures following injection of para-sternal solution prior to surgical incision. Patients are considered part of the research study until they are discharged. After discharge, patients can be told which block they were given and the blinded coordinator can be unblinded to review all medical records.

Study Population

Patients undergoing a surgical procedure through mini- or full sternotomy from 7/1/2019 at THHBP will be included in this data set. A total of 150 patients is proposed for this study.

Inclusion Criteria:

1. Age greater than 18 years
2. Undergoing a surgical procedure through mini- or full sternotomy.

Exclusion Criteria:

1. Clinical instability

2. Allergic to liposomal bupivacaine solution or any of its ingredients
3. Maximum-allowed dosage of local analgesia will be exceeded by the injection amount of liposomal bupivacaine used in this study (<50 kg).

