4. ICU LOS
5. Total LOS from date of sternotomy
6. Return of bowel function
7. Postoperative atrial fibrillation

8. Maximum spirometry at 24, 48, 72 hours post op
9. CAM at 24, 48, 72 hours post op
10. Pain Scores (Scale 0-10) at 1, 2, 4, 8, 12, 24, 36, 48, 60, and 72 hours after ICU arrival for extubated patients and CPOT scores (Scale 0-8) for intubated patients
11. Post op opioid usage up to 72 hours post op

Standard descriptive statistics will be used throughout (mean, range, standard deviation, and median, IQR), with comparative statistics for normally and non-normally distributed data with $p < 0.05$ considered as significant. For categorical variables, 2 Sample t-test or chi-squared test will be used to determine statistical significance. For continuous variables, logistic regression will be used to determine the value of significance to variables with postoperative outcomes. Depending on the enrollment rate, the stratification of data based on the type of sternotomy (full or mini) could be performed and analyzed respectively.

References

1. Bignami, E., et al., *Perioperative pain management in cardiac surgery: a systematic review*. Minerva Anestesiol, 2018. 84(4): p. 488-503.
2. Dowling, R., et al., *Improved pain control after cardiac surgery: results of a randomized, double-blind, clinical trial*. J Thorac Cardiovasc Surg, 2003. 126(5): p. 1271-8.
3. Barr, A.M., E. Tutungi, and A.A. Almeida, *Parasternal intercostal block with ropivacaine for pain management after cardiac surgery: a double-blind, randomized, controlled trial*. J Cardiothorac Vasc Anesth, 2007. 21(4): p. 547-53.
4. Lee, C.Y., et al., *A Randomized Controlled Trial of Liposomal Bupivacaine Parasternal Intercostal Block for Sternotomy*. Ann Thorac Surg, 2019. 107(1): p. 128-134.
5. Labrum, J.T.t. and A.M. Ilyas, *Preemptive Analgesia in Thumb Basal Joint Arthroplasty: Immediate Postoperative Pain with Preincision versus Postincision Local Anesthesia*. J Hand Microsurg, 2017. 9(2): p. 80-83.

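### Allocation is described only as a 1:1 spreadsheet-generated assignment, with no blocking, locked list or stratification by sternotomy type, and the comparison does not adjust for type.

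*Combined protocol and SAP*

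**What the plan says.** The Procedures paragraph under Methods contains the whole allocation method: "Qualified patients will be randomized 1:1 to a liposomal bupivacaine sternal block or a normal saline block", and "An unblinded research coordinator will use a password-protected spreadsheet to randomly generate" each subject's assignment. The coordinator then tells an unblinded anesthesiologist, who performs the block. The text gives no block size, list prepared in advance, minimisation or stratification factor. It does not say how the 1:1 ratio is held, or at what point relative to consent an assignment is revealed.

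Under Study Population, "A total of 150 patients is proposed for this study", and eligibility covers anyone "undergoing a surgical procedure through mini- or full sternotomy". The expected split between the two approaches is not given. The hypothesis pools them.

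Data Analytic Methods reports the between-arm difference in opioid use as one value and names t-tests, chi-squared tests and logistic regression, with no covariate specified for the treatment comparison. Type of procedure is listed among the variables, but sternotomy type is not named as an adjustment factor. The section closes by saying that, depending on enrolment, "the stratification of data based on the type of sternotomy (full or mini) could be performed and analyzed respectively".

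**The concern.** Sternotomy type is the only factor that the plan singles out for a possible separate analysis, and it plausibly affects pain and opioid use. The block is given before incision, so the planned approach should be known when a patient is randomised (an inference; the protocol does not say so). As written, type is used neither in the randomisation nor in the main comparison.

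Three things could follow if assignments are unrestricted draws:

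- the arms end up unequal in size;
- the full/mini mix differs between arms, which adds noise to an unadjusted contrast;
- a small mini group splits unevenly, just where the optional analysis would need it balanced.

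Separately, without a list fixed beforehand there is no record against which to confirm that each assignment was used as generated.

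**Working it through.** **Inputs.** From the protocol: N = 150, ratio 1:1, both approaches eligible. Not in the protocol, so assumed: an unrestricted draw; a mini share s of 10% to 50%; two-sided alpha of 0.05 (the plan gives 0.05 without sidedness); and a design with 80% or 90% power at 75/75. The plan gives no effect size, SD or power behind the 150, so there is no figure of its own to reproduce.

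**Arm sizes.** With n1 ~ Binomial(150, 0.5), the difference between arms has SD √150 = 12.2 patients. Exact probabilities are 0.46 for a difference of 10 or more, 0.12 for 20 or more (65/85 or worse) and 0.018 for 30 or more (60/90 or worse).

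**Cost of unequal arms.** In SD units, SE = √(1/n1 + 1/n2).

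- 75/75: √(2/75) = 0.1633
- 65/85: √(1/65 + 1/85) = 0.1648, which is 0.9% larger
- 60/90: √(1/60 + 1/90) = 0.1667, which is 2.1% larger

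For 80% power at 75/75 the effect is (1.960 + 0.842) × 0.1633 = 0.457 SD. Power is then 79.3% at 65/85 and 78.4% at 60/90. A 90% design keeps 89.5% and 88.8%.

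**Full/mini mix.** With m = 150s mini patients, X ~ Binomial(m, 0.5) and Y ~ Binomial(150 − m, 0.5) are the mini and full counts in arm 1. The difference in mini share is |X/(X+Y) − (m−X)/(150−X−Y)|. Exact results:

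| Assumed mini share (m) | Share differs by ≥10 points, unrestricted | Same, arms fixed at 75/75 but not stratified | Mini group splits 60/40 or worse, unrestricted |
|---|---|---|---|
| 10% (15) | 0.04 | 0.03 | 0.61 |
| 20% (30) | 0.13 | 0.15 | 0.36 |
| 30% (45) | 0.18 | 0.15 | 0.23 |
| 50% (75) | 0.22 | 0.19 | 0.11 |

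A normal check agrees. At s = 20% the SD of the share difference is √(4 × 0.2 × 0.8/150) = 0.065, and 0.10/0.065 = 1.53, a two-sided probability of about 0.13. Equalising the arm sizes alone barely changes this risk; stratification or adjustment is needed.

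**Cost of a mix difference.** It depends on how far the two approaches differ in outcome, which the plan does not say. Call that difference d, in within-type SDs. A 10-point imbalance shifts the unadjusted contrast by 0.10 × d:

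- d = 0.5: 0.05/0.163 = 0.3 SE
- d = 1: 0.10/0.163 = 0.6 SE

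Averaged over all allocations, leaving type out of the analysis inflates the SE by √(1 + s(1 − s)d²):

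- d = 0.5: √1.04 = 1.02 at s = 20%; √1.0625 = 1.03 at s = 50%
- d = 1: √1.16 = 1.08 at s = 20%; √1.25 = 1.12 at s = 50%

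**Mini subgroup.** With 30 mini patients, a 10/20 split or worse has probability 0.099. Its SE is √(1/10 + 1/20) = 0.387, against √(2/15) = 0.365 at 15/15, or 6% larger.

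**After the fix.** Stratified blocks of 4 limit the arm difference to 2 per stratum and 4 overall. Blocks of 4 and 6 limit it to 3 and 6 (half the largest block, in each of two strata).

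**The case against.** The strongest reply is that the protocol is silent, not wrong. A reader might infer that it states simple randomisation, drawn on the spot. It does not. The wording leans towards a draw per subject, but a password-protected spreadsheet could equally hold a blocked list made in advance. The probabilities above therefore apply only if the draw is unrestricted.

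A reader might also infer that the plan commits to analysing by sternotomy type. It says only that this could be done, depending on enrolment.

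On consequences, much of the objection stands. Arm-size drift costs under 2 points of power even at 60/90. Chance imbalance causes no bias on average, and the ordinary SE already reflects it. In a mini group of 30, the small number of patients limits precision far more than an uneven split does. Adjusting for type would recover most of the lost precision without touching the randomisation. Blocks within strata are also somewhat easier to guess, and here the coordinator and the anesthesiologist performing the block both know past assignments.

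What remains is that the method is unspecified either way, and that no adjustment for type is named.

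**Conclusion.** The point holds as a gap in specification that is cheap to close. It is not a flaw that threatens the trial's validity. The protocol describes no blocking, locked list or stratification by sternotomy type, and the main comparison names no adjustment for type, although both types are enrolled.

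If the draw is unrestricted, a difference of 10 points or more in mini share has probability of about 13% to 22% for assumed mini shares of 20% to 50%, and about 4% at 10%. The resulting loss of precision is modest: 2% to 12% on the SE for assumed differences between types of 0.5 to 1 SD at mini shares of 20% to 50%. That type affects the outcome at all is plausible but not documented. The full/mini mix and the absence of a described fixed sequence carry the point. Arm-size drift does not.

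**What to change.** In Procedures, state that before enrolment one computer-generated list will be produced and locked, using permuted blocks of randomly varying size (for example 4 and 6), stratified by planned full versus mini sternotomy. State that the unblinded coordinator reveals the next entry only after eligibility and consent are recorded. In Data Analytic Methods, include planned sternotomy type as a factor in the opioid and pain comparisons.

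The cost is a sentence or two of protocol text, a two-stratum list prepared once, and one model term. There are two downsides. Patients whose approach changes stay in their planned stratum. Blocks are slightly more predictable to the unblinded staff; varying the block size limits this without removing it. Stratification cannot be added for patients already randomised. If only one change is made, prespecify the adjustment.

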11. CKD
12. CVA
13. Chronic home NSAID use (excluding ASA)

Intraoperative Variables:

1. Type of procedure being performed
2. Prior procedures performed

Postoperative Variables:

Time to extubation, time to ambulation, time to oral diet, return of bowel function (bowel movement), postoperative atrial fibrillation incidence (through discharge), and intensive care unit (ICU) length of stay (LOS) and overall LOS. Maximum incentive spirometer maximum volume at 24, 48 and 72 hours, Confusion assessment method (CAM) at 24, 48 and 72 hours, post op opioid usage up to 72 hours post op. If additional days of post-op opioid usage is documented in the existing medical record, this may be used also. CAMs are performed by the blinded research coordinator.

Pain scores (Scale 0-10) at 1, 2, 4, 8, 12, 24, 36, 48, 60, and 72 hours after ICU arrival for extubated patients and CPOT scores (Scale 0-8) for intubated patients

Adverse Events: Allergic reaction, pneumothorax, pericardial tamponade, vascular injury, hematoma, intravascular injection, wound infection, paresthesia, persistent numbness. These adverse events will be monitored and reported from the start of the study procedure to discharge (study termination).

Protocol Deviations: If certain data elements are not in the existing medical record and were not collected, this is not a protocol deviation. Nevertheless, all effort will be made to collect these data points.

Funding: CVRRC

Journals in which you plan to publish or meetings where abstracts will be submitted: TBD

Risks and Benefits

Risks: The risks are the same as the Standard of Care surgery performed outside this study. This is discussed in the ICF. A confidentiality breach is a risk associated with research. However, all data collection protocols follow HIPAA guidance.

Benefits: If participants receive the drug, they could experience less pain than those that don't receive the drug. However, not all participants are likely to benefit from the proposed research. The investigators will benefit from the knowledge gained, as it will provide deepened insight on the main challenges, advantages and disadvantages of the procedure.

Data Analytic Methods

The mean, standard deviation, median, and interquartile ranges of narcotic usage (in morphine equivalent units) will be reported for each group. The difference of narcotic usage between the two groups will be reported as a single value. Additional variables analyzed in this study include the following:

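### Procedures lets the blinded coordinator be unblinded after discharge to review records, without requiring that the patient's outcome data be completed blind first

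*Combined protocol and SAP*

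**What the plan says.** During the hospital stay the blind is well set out. Procedures provides separate blinded and unblinded anesthesiologists and coordinators, and says that "postoperative staff (including the blinded research coordinator) will remain blind to the randomization assignment". Of the patient it says "The subject will also be blinded to the assignment".

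The same section then says when the blind may end: "After discharge, patients can be told which block they were given and the blinded coordinator can be unblinded to review all medical records". The trigger is discharge. The sentence does not say whether the coordinator is unblinded patient by patient or once after the last patient, and it sets no condition on the state of the data.

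Three other places bear on what a record review might involve:

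- **Data elements, Postoperative Variables.** One outcome is expressly given to a blinded assessor: "CAMs are performed by the blinded research coordinator". On opioid use after 72 hours, the section says "If additional days of post-op opioid usage is documented in the existing medical record, this may be used also".
- **Protocol Deviations.** "If certain data elements are not in the existing medical record and were not collected, this is not a protocol deviation". The next sentence adds: "Nevertheless, all effort will be made to collect these data points".
- **Data Analytic Methods.** "The mean, standard deviation, median, and interquartile ranges of narcotic usage (in morphine equivalent units) will be reported for each group". The section names the unit but not who converts doses to it, when, or under what blind.

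**The concern.** Pain scores and postoperative opioid use are both Aim 1 outcomes. The trial protects them during the stay with a saline block and a split between blinded and unblinded staff. The unblinding sentence lets that protection end, for the coordinator, before the data need be final, and gives record review as the reason.

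If outcome work remains at that point, someone who knows the arm could choose which charted pain score stands for a scheduled time, how hard to search for a missing value, and whether later opioid days are used. At the end of the trial, bias from that step could not be ruled out, because the final data set would not show whether the choices were made blind.

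**Working it through.** The plan gives no figure to reproduce. The check is a reading of the sections against each other, followed by a count of the data that could at most be affected.

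**1. Is the permission real?** Yes. Procedures states it in terms, and record review is its declared purpose. It is a permission, not an instruction.

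**2. Does any section attach a condition?** Hypothesis/Aims, Methods, Procedures, Data elements, Protocol Deviations and Data Analytic Methods contain no data lock, no rule that abstraction be finished or done blind, no rule on who converts opioid doses, and no blinded analyst.

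**3. What is protected regardless?** The source entries. Pain scores, opioid doses and CAM results arise during the stay, when patient and postoperative staff are to be blind. Later unblinding of the coordinator does not alter what was charted.

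**4. Which later steps leave room for judgement?**

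| Step | Room for judgement if done after unblinding |
|---|---|
| Matching pain scores to scheduled times | Some: ten times are listed without windows, and Aim 1 speaks of daily scores |
| Searching the record for missing values | Some: effort is promised but not bounded, and a missing element is not a deviation |
| Using opioid data beyond 72 hours | Some: optional, with no rule |
| Totalling opioids in morphine equivalents | Limited: arithmetic once doses and factors are fixed, but no factors are given |
| Extubation time, spirometry volume, ICU and total length of stay | Little |
| Bowel function, atrial fibrillation | Little: the first is defined as a bowel movement, the second as incidence to discharge |

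The missing time windows and conversion factors are separate gaps. They matter here only because they show that abstraction is not purely mechanical.

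**5. How much data, at most?**

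- Patients: 150 (Study Population).
- Scheduled pain assessments per patient: at 1, 2, 4, 8, 12, 24, 36, 48, 60 and 72 hours after ICU arrival, which is 10 (Postoperative Variables).
- Pain values: 10 × 150 = 1,500.
- Postoperative opioid totals: 1 × 150 = 150.

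These are all the scheduled pain values and all the postoperative opioid totals in the trial. The number actually left for work after discharge is unknown and could be close to zero.

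**The case against.** The strongest reply is that nothing says outcomes are abstracted at the post-discharge review. What the plan says about timing points the other way: Aim 1 has opioid use recorded during the postoperative course and pain scores obtained daily, and Aim 3 has its variables recorded in the postoperative setting. The unblinding sentence may even be a safeguard, keeping the full chart from the coordinator until that patient's CAMs are done. The Protocol Deviations text can also be read as treating the medical record and study collection as two separate sources, which fits collection during the stay equally well. These points stand. They show that unblinded abstraction is an inference, not a stated plan. They do not supply the missing condition: no section says that collection must be finished before the coordinator is unblinded.

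It is also fair to say that a lock would not cure the undefined time windows, the missing conversion factors or the loose opioid window. That stands too. Those need their own rules. The lock only ensures that whatever discretion remains is exercised blind.

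A reader might infer three stronger things, none of which the documents support:

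- **That the trial will abstract its outcomes unblinded.** The text allows this but does not say it.
- **That 1,500 and 150 measure the problem.** They are ceilings on exposure and say nothing about the amount or direction of bias.
- **That CAM on later patients is compromised because the coordinator knows earlier assignments.** Each patient's own CAMs come before that patient's discharge. An effect on later patients would need patient-by-patient unblinding and, beyond that, assignments that become predictable. Procedures leaves the first open and describes only random generation from a spreadsheet, with no blocking stated.

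**Conclusion.** The point holds in a limited form. The plan expressly permits the blinded coordinator to be unblinded after discharge to review records, and does not require that patient's outcome data to be completed first. The exposure is confined to abstraction and derivation done after discharge, mainly the matching of pain scores to times, the search for missing values and the optional use of later opioid data. Opioid totalling is exposed to a lesser degree.

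The conclusion rests on one assumption that the documents neither confirm nor exclude: that some of this work is still open when the coordinator is unblinded. If none is, there is no bias from this source and the amendment only records existing practice. If some is, the bias is of unknown size and may be negligible; the documents give no basis for an estimate. This is a cheap improvement, not a flaw that undermines the trial.

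**What to change.** Amend the unblinding sentence in Procedures to name who abstracts outcomes. It should also require that each patient's outcome data be abstracted, converted to morphine equivalents and locked by blinded staff before that patient's assignment is disclosed to the blinded coordinator. The existing unblinded coordinator can tell discharged patients which block they had and handle any record that shows it. Keeping the blind until every patient's data are locked is optional.

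The cost is one amended sentence, somewhat later full-record access for the blinded coordinator and a little work for the unblinded one. The size of that work is uncertain, because the documents do not say where the block is charted. It is probably small: postoperative staff are to stay blind during the stay, which suggests that the working chart does not show the assignment. Treatment, visits, sample size and endpoints are unchanged.
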